9.7 Clinical Laboratory Evaluations

Standard clinical laboratory profiles for blood biochemistry, hematology, coagulation, and urinalysis will be evaluated at the local laboratory at Screening and at the local laboratory (Japan sites) and central laboratory (US sites) prior to study drug administration on dosing days (Day 1 and at Weeks 4, 8, and 12) and at Weeks 1, 2, 6, 10, 14, 16, 20, 24, and 28. Samples for evaluation by the central laboratory may be collected by home healthcare services (United States only) at non-dosing day visits. See Appendix B for a complete list of laboratory analytes.

9.8 Vital Signs

Vital signs (systolic and diastolic blood pressure, pulse rate, and body temperature) will be taken in the supine or sitting position after resting at Screening; prior to study drug administration on dosing days (Day 1 and at Weeks 4, 8, and 12); within 1 hour of the end of the infusion on Day 1; and at Weeks 1, 2, 3, 5, 6, 7, 9, 10, 11, 13, 14, 15, 16, 17, 18, 19, 20, 21, 22, 23, 24, 26, and 28. Vital signs may be taken by home healthcare services (United States only) at non-dosing day visits.

9.9 Electrocardiograms

A 12-lead ECG will be performed in a supine position after resting at Screening; prior to study drug administration at Weeks 4, 8, and 12; and at Weeks 16, 20, 24, and 28. Additional follow-up ECGs may be performed if clinically indicated. A 12-lead ECG may be performed by home healthcare services (United States only) at non-dosing day visits.

9.10 Physical Examinations

A complete physical examination will be performed at Screening; prior to study drug administration on dosing days (Day 1 and at Weeks 4, 8, and 12); within 1 hour of the end of the infusion on Day 1; at Weeks 1, 2, 3, 16, 20, 24, and 28; and at the initiation of the Rescue Phase. A physical examination may be performed by home healthcare services (United States only) at non-dosing day visits.

9.11 Cytomegalovirus Serology

Cytomegalovirus serology will be tested using an enzyme immunoassay to detect CMV antibodies (immunoglobulin G) at Screening. Cytomegalovirus serology will be tested at the local laboratory within 90 days of Randomization to determine eligibility for the study.

9.12 Serum NPC-21 Concentration Measurement

Blood will be drawn on Day 1 and at Weeks 1, 2, 3, 4, 6, 8, 10, 12, 14, 16, 20, 24, and 28 for serum NPC-21 concentration measurement. On dosing days (Day 1 and at Weeks 4, 8, and 12), blood samples will be collected within 2 hours prior to study drug administration and at 2 hours (\pm 30 minutes) following the beginning of the infusion (Note: Sample collection time points at each visit may be updated based on each administration data). Samples may be collected by home healthcare services (United States only) at non-dosing day visits.

10 STATISTICS

Summary statistics will be presented by treatment group. Unless otherwise stated, continuous variables will be summarized by using the number of non-missing observations, arithmetic mean, standard deviation, median, minimum, and maximum values as descriptive statistics. Categorical variables will be summarized by using the frequency count, the percentage of patients with 95% confidence intervals in each category as descriptive statistics. Statistical tests will be 2-sided at the $\alpha=0.05$ significance level. The procedures for handling missing, unused, or spurious data, along with the detailed method for analysis of each variable will be presented in the Statistical Analysis Plan.

Changes in study visit schedules, missed or delayed visits, or patient discontinuations and the relationship to COVID-19 will be captured in the eCRFs. Protocol deviations in study procedures due to COVID-19 will be reported in the Clinical Study Report.

10.1 Analysis Populations

The Intent-to-Treat Population will include all randomized patients.

The modified Intent-to-Treat (mITT) Population will include all patients who receive a kidney transplant from a living or deceased donor and receive at least 1 dose of study drug (6 mg/kg NPC-21, 12 mg/kg NPC-21, or placebo). The mITT Population will be used for all efficacy analyses.

The PK Population will include all patients who receive any amount of study drug (6 mg/kg NPC-21, 12 mg/kg NPC-21, or placebo) and have evaluable PK data. The PK Population will be used for the PK analyses and exposure-response analyses.

The Safety Population will include all randomized patients who receive at least 1 dose of study drug (NPC-21 or placebo). The Safety Population will be used for safety analyses.

10.2 Statistical Methods

10.2.1 Analysis of Efficacy

The mITT Population will be used for all efficacy analyses.

The primary efficacy endpoint will be the proportion of patients with the occurrence of CMV disease (CMV syndrome [see Appendix C for definition of CMV syndrome] or tissue-invasive CMV disease [see Appendix D for definitions of CMV disease]) or CMV viremia (defined as the detection of ≥ 250 IU/mL in plasma measured by PCR analysis in central laboratory or meets the local criteria for CMV viremia measured by PCR analysis or antigenemia testing) by Week 16. Non-responders will include all patients who develop CMV disease or CMV viremia. In principle, patients who discontinue from the study prior to Week 16 in the absence of CMV disease or CMV viremia will be considered as non-responders. If warranted under special circumstances, a patient who discontinues from the study prior to Week 16 may be discussed with the medical expert to determine status as a responder or non-responder. If this occurs, the rationale for considering the patient as a responder will be finalized before database lock and documented in the Statistical Analysis Plan. Sensitivity analysis may be performed to assess the impact of these patients on analysis results.

The primary efficacy endpoint will be summarized by treatment group and compared across placebo and the 6 mg/kg NPC-21 treatment group using a logistic regression analysis with stratification factor of region (United States or Japan) as a covariate.

Other efficacy endpoints will be summarized descriptively by treatment group using the mITT Population.

10.2.2 Analysis of Pharmacokinetics

Serum concentrations of NPC-21 will be summarized using descriptive statistics. In addition, analysis of the concentration data as part of population-PK modeling will be described in a separate PK Analysis Plan and reported separately.

10.2.3 Analysis of Exposure-Response

Exposure-response analyses will be performed to propose target concentrations using PK parameters estimated by population-PK, efficacy variables, and biomarkers.

10.2.4 Analysis of Safety

The Safety Population will be used for all safety analyses. Safety will be summarized descriptively by treatment group.

Descriptive summary statistics will be provided for all safety variables, including 12-lead ECGs, vital signs, clinical laboratory assessments, and adverse events reported during the study.

The number and percentage of patients experiencing treatment-emergent adverse events will be summarized. Summaries will be produced for each body system, as well as for each preferred term using the Medical Dictionary for Regulatory Activities. The number and percentage of patients experiencing SAEs will also be summarized.

10.2.5 Interim Analysis

No interim analysis is planned.

10.2.6 Data and Safety Monitoring Board

The safekeeping and monitoring of data collection will be performed by an independent third party DSMB. The DSMB will be independent of the Sponsor, contract research organization, study Investigators, and anyone involved in the care or evaluation of study patients. Members of the DSMB will not have scientific, financial, or other conflicts of interest related to the Sponsor or Investigators.

The DSMB will meet to review unblinded aggregate and individual patient data related to safety, data integrity, and overall conduct of the study and will provide recommendations to continue, temporarily halt, modify, or terminate the study based on data analysis. The committee may communicate other recommendations or concerns as deemed appropriate. Additional information will be provided in the DSMB charter as approved by the members.

10.2.7 Sample Size Determination

A total sample size of approximately 108 patients is planned for the study, with a 1:1 randomization ratio for 6 mg/kg NPC-21 versus placebo and another 12 patients for high-level

dose of 12 mg/kg NPC-21 (4:1:4 randomization ratio for 6 mg/kg NPC-21, 12 mg/kg NPC-21, or placebo). The sample size calculation is based on the mITT Population from the first dose of NPC-21 through Week 16 for the occurrence of CMV disease (CMV syndrome or tissue-invasive CMV disease) or CMV viremia (defined as the detection of ≥ 250 IU/mL in plasma measured by PCR analysis in central laboratory or meets the local criteria for CMV viremia measured by PCR analysis or antigenemia testing) primary endpoint. Assuming an early discontinuation rate of 15%, approximately 48 patients each in the 6 mg/kg NPC-21 and placebo arms are needed with a 2-sided significance level of 0.05 and a power of 80% to detect a difference between NPC-21 at a predicted incidence rate of CMV disease (CMV syndrome or tissue-invasive CMV disease) or CMV viremia of 30% versus 60% for placebo. In addition, a sample size of 12 patients for the 12 mg/kg NPC-21 arm is considered adequate for the planned exposure-response analysis.

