4.3 Withdrawal Criteria

Patients may be discontinued from study drug for any of the following reasons:

- The patient no longer meets all inclusion criteria or meets any exclusion criteria and is found to be ineligible for participation through procedures (eg, medical examinations) performed after Randomization.
- Occurrence of any medical condition or circumstance that exposes the patient to substantial risk and/or does not allow the patient to adhere to the requirements of the protocol.

- Any SAE, clinically significant adverse event, severe laboratory abnormality, intercurrent illness, or other medical condition that indicates to the Investigator that continued participation is not in the best interest of the patient.
- Pregnancy.
- Requirement of the following therapy:
 - CMV hyperimmune globulin (eg, CytoGam®).
 - IVIg.
 - Plasmapheresis.
- Patient failure to comply with protocol requirements or study-related procedures and the Investigator considers it inappropriate to administer the study drug.
- Initiation of Rescue Phase.

Patients who discontinue study drug for any reason should be followed per the study schedule of events until the end of study participation.

Participation of a patient in this clinical study may be discontinued for any of the following reasons:

- The patient withdraws consent or requests discontinuation from the study for any reason.
- Termination of the study by the Sponsor or the regulatory authority.
- If a patient develops COVID-19 and is unable to continue with study visits and observations, the patient should be discontinued from the study and standard of care CMV treatment should be initiated, if necessary. If COVID-19 treatment will be provided to the patient, the Investigator should notify the Medical Monitor prior to study discontinuation, if possible. All patients should be followed for safety and resolution of COVID-19 infection. Patients who are able to complete study-related visits as an outpatient or via home healthcare services (United States only) or are inpatient and can receive study treatment will be allowed to continue to participate in the study if they do not receive any experimental treatments for COVID-19.

In the case of patients lost to follow-up, attempts to contact the patient must be made and documented in the patient's medical records.

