3.3 Patient Data and Study Conduct

3.3.1 Patient Disposition

The following patient disposition categories will be summarized via counts and percentages by treatment group and in total for all screened patients:

- Patients who were screened
- Patients who were randomized
- Patients who were treated
- Patients who end study treatment and continued in the study for assessments
- Patients who end study treatment but discontinued in the study for assessments
 - Primary reason for discontinuation
- Patients who completed the study
- Patients who withdrew early from the study
 - Withdrew early from the study before Week 16
 - Withdrew early from the study after Week 16
 - Primary reason for early withdrawal
- Patients who entered rescue phase
 - Reason for entering rescue phase

All patient disposition data will be listed by-patient.

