1 INTRODUCTION

The statistical analysis plan (SAP), version 1.0, for the study with protocol number NPC-21-2 was finalized on 29 March 2023.

The final database lock for this study was on 30 March 2023 with last signature data lock approval on 03 April 2023. Further updates to the planned analysis are documented in this addendum.

Summary of changes:

- Updated the analysis methods of some secondary and exploratory endpoints

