2 DATA ANALYSIS CHANGES

2.1 Categorical Endpoints

In SAP version 1.0, section 3.4.2.1 describes that the categorical endpoints are analyzed using the same analysis method as the primary endpoint.

However, for the analysis of primary endpoint, the non-responders include all patients who develop CMV disease or CMV viremia and patients who discontinue from the study prior to Week 16 in the absence of CMV disease or CMV viremia.

This SAP addendum further clarifies that for the endpoints below, patients who discontinued from the study prior to Week 16 in the absence of CMV disease would not be considered as non-responders:

- Incidence of CMV disease by Week 16
- Incidence of CMV disease by Week 28

For the endpoints below, patients who discontinued from the study prior to Week 16 in the absence of CMV viremia would not be considered as non-responders:

- Incidence of CMV viremia by Week 16
- Incidence of CMV viremia by Week 28

For the secondary endpoint “Incidence of CMV disease or CMV viremia by Week 28”, the same analysis method as the primary endpoint is used by still including patients who discontinued from the study prior to Week 16 in the absence of CMV disease or CMV viremia as non-responders.

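### The 80% power appears to assume that the 15% early discontinuers drop out of the analysis, but the primary analysis counts them as failures; on that rule 48 per arm gives about 71-74%

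*Protocol*

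**What the plan says.** Protocol section 10.2.7 defines the basis of the calculation: "The sample size calculation is based on the mITT Population from the first dose of NPC-21 through Week 16". The assumed incidences of CMV disease or viremia are 30% on 6 mg/kg NPC-21 and 60% on placebo, "with a 2-sided significance level of 0.05 and a power of 80% to detect a difference". It then gives the size: "Assuming an early discontinuation rate of 15%, approximately 48 patients each in the 6 mg/kg NPC-21 and placebo arms are needed". The synopsis and SAP section 2.2.4 carry the same text. None of the three names a formula, says how the 15% enters, gives the period the 15% covers, or says whether it is the same in both arms.

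The primary analysis is a logistic regression with region as covariate in the mITT Population (transplanted patients who received at least one dose). For discontinuers, Protocol section 10.2.1 sets this default: "patients who discontinue from the study prior to Week 16 in the absence of CMV disease or CMV viremia will be considered as non-responders". SAP section 3.4.1 repeats it. Both allow a medical expert to reclassify a patient in special circumstances. Section 2.1 of the SAP addendum confirms that the default governs the primary analysis: "the non-responders include all patients who develop CMV disease or CMV viremia and patients who discontinue from the study prior to Week 16".

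Two other places bear on what the 15% means. Protocol section 4.3 keeps patients who only stop treatment under observation: "Patients who discontinue study drug for any reason should be followed per the study schedule of events until the end of study participation". SAP section 3.3.1 reports early withdrawal separately before and after Week 16, the first category being "Withdrew early from the study before Week 16".

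**The concern.** Inflating a sample size for dropout preserves power only if the dropouts leave the denominator and the remaining patients keep the assumed event rates. Here they stay in the denominator and are scored as failures. That raises the analysed failure rate in both arms and, when discontinuation is equal and unrelated to outcome, shrinks the difference between them. The extra patients do not offset this, because the effect being tested has become smaller.

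If the 48 was built by removing discontinuers, the stated 80% does not describe the analysis that will be run. A reader of a non-significant result would then credit the trial with more sensitivity than it was designed to have.

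**Working it through.** **Inputs.** From Protocol section 10.2.7: two-sided alpha 0.05 (z = 1.96), power 80% (z = 0.8416), rates 0.30 and 0.60, 1:1 allocation, 15% discontinuation, 48 per arm. From Protocol section 10.2.1 and SAP section 3.4.1: event-free leavers before Week 16 count as failures.

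**Reproducing the 48.** With the unpooled normal approximation:

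n = (1.96 + 0.8416)² × (0.30×0.70 + 0.60×0.40) / 0.30² = 39.24, rounded up to 40.

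40 / 0.85 = 47.06, rounded up to 48, which matches the plan. The pooled-variance formula gives 41.97, so 42, and 42 / 0.85 = 49.4, so 50. As a cross-check, 48 × 0.85 = 40.8; 41 evaluable patients per arm give 79.0% (pooled) to 81.7% (unpooled).

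**Applying the planned rule.** Assume 15% leave each arm before Week 16, independently of outcome, with no reclassification. The analysed failure rate is p + (1 − p) × 0.15:

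- NPC-21: 0.30 + 0.70×0.15 = 0.405
- Placebo: 0.60 + 0.40×0.15 = 0.660
- Difference: 25.5 points instead of 30

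Power at 48 per arm:

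- Unpooled: standard error = √[(0.405×0.595 + 0.66×0.34)/48] = 0.0985; 0.255/0.0985 − 1.96 = 0.63; power 73.6%.
- Pooled: mean rate 0.5325; [0.255×√48 − 1.96×√(2×0.5325×0.4675)] / √0.4654 = 0.56; power 71.3%.
- Exact enumeration of the Pearson chi-square test: 72.1%.
- Simulated logistic regression with region (20,000 replicates per scenario; assumed Japan share 25% or 50%, assumed regional rate difference 0, 10 or 20 points): 71.5-73.1%.

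On these rates, 80% power would need 57 (unpooled) to 59 (pooled) per arm.

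**Range over the unstated inputs**, 48 per arm, pooled to unpooled. True incidences are 30% versus 60% unless the row says otherwise.

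| Scenario | Analysed rates, NPC-21 vs placebo | Power |
|---|---|---|
| 15% in each arm | 40.5% vs 66.0% | 71.3-73.6% |
| 10% in each arm | 37.0% vs 64.0% | 76.2-78.5% |
| 8.6% in each arm (15% × 16/28, spread evenly over 28 weeks) | 36.0% vs 63.4% | 77.5-79.8% |
| 5% in each arm | 33.5% vs 62.0% | 80.8-83.1% |
| 18% NPC-21, 12% placebo | 42.6% vs 64.8% | 59.0-60.9% |
| 12% NPC-21, 18% placebo | 38.4% vs 67.2% | 81.7-83.9% |
| True NPC-21 incidence 28%, 15% in each arm | 38.8% vs 66.0% | 76.9-79.2% |
| True NPC-21 incidence 27%, 15% in each arm | 37.95% vs 66.0% | 79.5-81.7% |
| 15% of all patients leave event-free, on top of 30%/60% | 45% vs 75% | 86.3-88.3% |
| 30%/60% already include discontinuers | 30% vs 60% | 85.1-87.3% |

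For the last row, exact Pearson power is 85.4%, simulated logistic power is 85.4-86.2%, and Fisher's exact test has 80.0%.

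**The case against.** The method is inferred, and the inference is not unique. The pooled formula leads to 50, not 48. There is also an uninflated route to exactly 48: it is the smallest size at which Fisher's exact test reaches 80% for 30% versus 60% (78.6% at 47, 80.05% at 48). If 30% and 60% already score discontinuers as failures, the stated power has a coherent and conservative basis.

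The 71-74% also needs several conditions together: all 15% leave the study (not just the drug) before Week 16, equally in both arms, independently of outcome, and no one is reclassified by the medical expert. If only 7.5% end up counted as event-free failures, power is 78.5-80.8%. If event-free leavers come on top of the 30% and 60%, it is 86-88%. Finally, with the data locked, the confidence interval for the difference tells a reader more than revised planning power does.

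Part of this stands. The method is unknown, so the conclusion must stay at appears, and 71-74% is conditional. But the Fisher route leaves the 15% in the sentence with no role, uses a test the plan does not use, and sits badly with text that calls 30% and 60% CMV incidences. Uncertainty in both directions does not support the stated 80%; it shows that the figure depends on definitions the plan does not give. The interval will indeed carry the inference, but a published power statement should still match the analysis it describes.

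**Conclusion.** The concern holds. The 80% is not shown to be a property of the planned primary analysis. On the most natural reading of the text (30% and 60% are true CMV incidences and 15% leave each arm before Week 16, independently of outcome, all scored as failures), power is about 71-74%, a shortfall of roughly 6 to 9 points. On the alternative reading, where the rates already include discontinuers, it is about 85-87%. Which applies turns on facts only the sponsor has. The consequence is limited to how the design is described and how a non-significant result is read; Type I error, the primary test and the estimate are unaffected.

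**What to change.** Restate the power for the planned analysis. The affected places are Protocol section 10.2.7, the synopsis and SAP section 2.2.4. The SAP addendum records that "The final database lock for this study was on 30 March 2023", so a further addendum or the study report is the practical vehicle. It should give the formula or software method, the period the 15% covers and whether it means leaving the study, and whether 30% and 60% include discontinuers.

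If they are true CMV incidences, wording such as this would do:

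> With 48 patients per arm, true incidences of 30% and 60%, and 15% of each arm discontinuing the study before Week 16 independently of outcome and counted as non-responders, the analysed rates are 40.5% and 66.0% and power is about 71-74%. Power of 80% corresponds to a true NPC-21 incidence of about 27% against 60%.

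If the rates already include discontinuers, say so, drop the 15% inflation and state about 85-87% for a chi-square or logistic test.

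The cost is wording only, with no change to enrolment, conduct or analysis. On the first reading the stated power becomes less favourable.

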11 DATA MANAGEMENT AND RECORD KEEPING

11.1 Data Management

11.1.1 Data Handling

Data will be recorded at the site on eCRFs and reviewed by the CRA during monitoring visits. The CRAs will verify data recorded in the EDC system with source documents. All corrections or changes made to any study data must be appropriately tracked in an audit trail in the EDC system. An eCRF will be considered complete when all missing, incorrect, and/or inconsistent data have been accounted for.

11.1.2 Computer Systems

Data will be processed using a validated computer system conforming to regulatory requirements.

11.1.3 Data Entry

Data must be recorded using the EDC system as the study is in progress. All site personnel must log into the system using their secure user name and password in order to enter, review, or correct study data. These procedures must comply with Title 21 of the Code of Federal Regulations (21 CFR Part 11) and other appropriate international regulations. All passwords will be strictly confidential.

